12.3 Safety analysis

Following standard procedures, frequency and severity measures of side effects will be constructed from the clinical measures. Descriptive statistics as well as changes from baseline will be presented by study group at each scheduled visit.

13.0 Provisions to Monitor the Data to Ensure the Safety of Subjects

1. *Trial Management:* The study will be managed from the Brain Stimulation Lab within the Department of Psychiatry and Behavioral Sciences at the Medical University of South Carolina.
2. *Data Management and Analysis:* Data will be entered by research assistants directly into a computer using standard database software. The data analysis plan is outlined in the Data Analysis Plan section.
3. *Quality Assurance:* The PI will have weekly meetings with the research assistants to discuss qualitative comments received during data collection and any problems in data collection. The statistician will periodically examine the database to look for irregularities. Initial data analyses will examine distributions of variable scores, and comparability of baseline characteristics across conditions in case analyses need to be adjusted for these. Confidentiality protections are outlined above.
4. *Regulatory Issues:* All unexpected Adverse Events (AEs) will be reported to the MUSC IRB and Committee on Human Research within 48-business hours. Serious AEs will be reported within 24-business hours. Follow-up of all unexpected and serious AEs will also be reported to these agencies.

5. *Definition of AE and SAE:* An AE is defined as any untoward medical occurrence in a study subject administered a pharmaceutical product that does not necessarily have a causal relationship with this treatment (ICH GCP). Any unwanted change, physically, psychologically or behaviorally, that occurs in a study participant during the course of the trial is an adverse event. A Serious Adverse Event (SAE) is defined as an adverse event that has one of the following outcomes: death, life-threatening, inpatient hospitalization or prolongation of existing hospitalization, persistent or significant disability/incapacity, a congenital anomaly/birth defect.
6. *Documentation and Reporting:* AEs/SAEs are documented and reported as per IRB requirements. Research staff will identify adverse events and obtain all available information to assess severity, seriousness, study relatedness, expectedness, outcome and the need for change or discontinuation in the study intervention. Adverse events are generally documented on AE Logs and AE Case Report Forms (CRFs). Additional relevant AE information if available will be documented in a progress note in the research record as appropriate to allow monitoring and evaluating of the AE. If the AE meets the definition for serious, appropriate SAE protocol specific reporting forms are completed and disseminated to the appropriate persons and within the designated timeframes as indicated above. For each AE/SAE recorded, the research staff will follow the AE/SAE until resolution, stabilization or until the participant is no longer in the study as stated in the protocol. We will report adverse events to the Medical MUSC IRB online per the IRB's guidelines.
7. *Study endpoints proposed:* The study is considered completed with the last visit of the last subject undergoing the study. Safety concerns, including a high rate of seizures (5%) can cause early study termination.

14.0 Withdrawal of Subjects *A subject will be withdrawn from the study for any of the following reasons:*

1. Withdrawal of consent
2. Subject is not compliant with requirements of the study, including inclusion criteria and exclusion criteria
3. The study is prematurely stopped
4. The investigator believes that for safety reasons it is in the best interest of the subject to stop treatment.
5. Subject motor threshold cannot be located.
6. Subject voluntarily withdraws from the study without reasons.
7. When a subject withdraws before completing the study, the reason for withdrawal will be documented on the CRF.

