1.1. Primary objective

To assess a feasibility of the rTMS for smoking cessation in cancer patients: The primary feasibility measures are (1) whether or not we can enroll 20 cancer patients with smoking within 12 months? (2) Study attrition. How many subjects can complete 7-day quit attempt during rTMS treatment? How many subjects will complete one-month follow-up? (3) To measure the percent completion of assessment measures.

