4.0 Study Endpoints

4.1 Primary efficacy endpoint

Conducting feasibility includes: (1) how many cancer patients with smoking can be enrolled in 12 months. (2) Study attrition. How many subjects can complete 7-day quit attempt during rTMS treatment. How many subjects will complete one-month follow-up. (3) Measurement strategy- percent completion of assessment measures.

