12.2 Data analysis

General considerations: All data will be analyzed in consultation ([name]) with the electronic system called REDCap (Research Electronic Data Capture). Statistical analyses will be performed using SPSS 22.0 (IBM Inc.). Baseline demographic and baseline characteristics, together with safety analyses will be performed on all enrolled subjects. Baseline values are defined as the measures on screening visit. The standard summary statistics for continuous variables are: mean, standard deviation, median, minimum and maximum. The standard summary statistics for categorical variables are: count and percentage. All statistical tests will be two-sided. For comparison of means (continuous variables), the two-sample t-test or the Wilcoxon rank sum test will be used as appropriate. For comparison of proportions (discrete data), the Chi-squared test will be used as appropriate. All test performed at significance $\alpha = 0.05$.

To assess a feasibility of the rTMS for smoking cessation in cancer patients: The numbers of subjects who were randomized and who entered and completed each visit of the study will be provided, as well as the reasons for all post-randomization discontinuations, grouped by treatment and by major reason. The discontinued subjects, protocol deviations, and subjects excluded will be provided as well.

To obtain the secondary estimates: The abstinence days, and cigarette consumption and cue-elicited craving will be compared between the active TMS and sham groups with a t-test or a repeated measures analysis of covariance model. Baseline daily number of cigarettes smoked, sex and center will be used as covariates.

To analyze the exploratory measures: cue-induced craving (QSU – Brief) and visual analog scale for craving will be measured pre and post each rTMS session. Other assessment, Carbon Monoxide, FTND, and MNWS-R will be compared between two groups.

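### Section 14.0 turns non-compliance and stopped treatment into withdrawal from the study, with no outcome collection afterwards and no efficacy analysis set

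*Combined protocol and SAP*

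**What the plan says.** Section 14.0 opens with a mandatory rule: "A subject will be withdrawn from the study for any of the following reasons". Three of the listed reasons are decided by staff:

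- Item 2: "Subject is not compliant with requirements of the study, including inclusion criteria and exclusion criteria". No threshold is given, and eligibility failures share the item with behaviour during the study.
- Item 4: "The investigator believes that for safety reasons it is in the best interest of the subject to stop treatment". A decision about treatment is thereby a ground for leaving the study.
- Item 5: "Subject motor threshold cannot be located". Section 10.3 has the threshold measured at entry but does not place this before or after randomisation.

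Sections 13.0 and 15.0 mention discontinuing the intervention, but neither says that outcome collection goes on afterwards. Section 13.0 lets adverse-event follow-up end once the participant has left the study.

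Attrition is a primary feasibility measure (sections 1.1 and 4.1): "How many subjects can complete 7-day quit attempt during rTMS treatment" and "How many subjects will complete one-month follow-up". Section 12.2 adds visit-by-visit counts, "as well as the reasons for all post-randomization discontinuations, grouped by treatment and by major reason", and then: "The discontinued subjects, protocol deviations, and subjects excluded will be provided as well".

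For analysis, section 12.2 names all enrolled subjects as the set for baseline and safety only. The comparison of abstinence days, cigarettes and craving has a test (t-test or repeated-measures analysis of covariance) but no analysis set and no rule for withdrawn participants. The models in section 12.1 have none either.

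**The concern.** Stopping stimulation and leaving data collection are different events, and section 14.0 makes the first a reason for the second. A participant removed on day 3 of the quit attempt would, on a literal reading, give no timeline for days 4 to 7 and no one-month call.

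Two things are at stake. The first is the secondary comparison, which Aim 2 presents as a preliminary estimate of efficacy. If those removed tend to be doing badly and more are removed from one arm, that arm looks better than it is. The second is the attrition count, which adds participants who chose to leave to participants whom staff removed. These answer different questions about whether the treatment is feasible in this population.

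**Working it through.** The plan states no expected attrition, effect size or standard deviation, so there is no figure of its own to reproduce. The check is a reading of the text, followed by illustrations of scale.

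**1. The text.** Section 14.0 requires study withdrawal under items 2 and 4. Section 4.4 schedules the one-month call, section 4.2 the self-reported timeline and section 10.2 the diary and CO. None of these says what happens after withdrawal. Section 12.2 does not say whether removed participants stay in the efficacy comparison. Section 4.2 scores 0 for anyone reporting no abstinent 24-hour period, without saying whether that covers withdrawn participants. Two teams could therefore follow the plan and treat the same participant differently.

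**2. Attrition.** N = 20 (section 6.0). Each imposed removal lowers the completion proportion by 1/20 = 5 points, so two lower it by 10 and three by 15. For scale, the exact 95% interval for 18/20 (90%) is 68.3% to 98.8%.

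**3. Outer bound on missing days.** Assume 10 per arm (the allocation ratio is not stated). If k participants in one arm have wholly unknown abstinence days (range 0 to 7), that arm's mean is uncertain over 7k/10 days: 0.7, 1.4 and 2.1 for k = 1, 2, 3. Days recorded before removal would narrow this.

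**4. A simple case.** Ten participants averaging 3 days total 30. If two with 0 days are dropped entirely, the mean becomes 30/8 = 3.75.

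**5. False difference with no true effect.** All inputs here are assumptions. Days follow a beta-binomial(7; 0.8, 1.0) distribution in both arms, with mean 7 × 0.8/1.8 = 3.11, P(0) = 0.178 and P(1) = 0.143, so about 32% have 0 or 1 day. A fraction r of that 32% is removed and dropped from the analysis. The arm's expected mean becomes

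(3.111 − 0.1426 r) / (1 − 0.3208 r).

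For r = 0.5 this is 3.040/0.840 = 3.62.

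| Removed among those with 0–1 day, arm A v arm B | Mean A | Mean B | False difference (days) |
|---|---|---|---|
| 50% v 0% | 3.62 | 3.11 | 0.51 |
| 75% v 25% | 3.96 | 3.34 | 0.61 |
| 50% v 25% | 3.62 | 3.34 | 0.28 |
| 20% v 10% | 3.29 | 3.20 | 0.09 |
| 50% v 50% | 3.62 | 3.62 | 0 |

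Simulation of 20,000 trials agrees to within about 0.01 day. The 50% v 0% row means about 10 × 0.32 × 0.5 = 1.6 removals in one arm and none in the other.

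**6. Scoring instead of dropping.** If the removed participants are scored 0, only those with 1 day change, and the shift is 0.1426 × (difference in r). That is 0.07 day for 50% v 0% and for 75% v 25%, and 0.04 for 50% v 25%, in the opposite direction.

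**7. Against sampling error.** Under the same model the variance is 7 × 0.8 × 1.0 × 8.8/(1.8² × 2.8) = 5.43, so the SD is 2.33 and the standard error of the arm difference is 2.33 × √(2/10) = 1.04 days.

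**The case against.** The case against has real weight.

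- **Attrition is largely covered.** Section 12.2 reports reasons for post-randomisation discontinuation by arm, and section 14.0 item 7 records the reason on the CRF. Imposed and voluntary losses can be separated from that table, and staff removals are genuine non-completions in a feasibility study. This stands. What remains is that the headline count does not make the split. A reader might infer that the attrition endpoint is uninterpretable; the documents do not support that.
- **Nothing says collected data are discarded.** This also stands. Days already recorded remain available, and the mixed model for cigarettes in section 12.1 can use partial records. The loss is of later data. It is inferred from study withdrawal together with the absence of any provision for continued collection.
- **Item 2 may be narrower than it looks.** It covers eligibility failures, and items 2 and 5 may apply before randomisation. Section 10.4 asks participants to abstain for as long as they can, so smoking is not in itself non-compliance. Section 10.3 lets missed sessions be made up within the 7 days. One might infer that a missed session or diary triggers removal, but no section says so. A link between non-compliance and smoking is plausible but is an assumption.
- **The larger illustrations need strongly unequal removal.** Blinding with an active sham makes unequal removal for non-compliance less likely, though safety stops could still differ by arm. Even 0.6 day is smaller than the standard error of about 1.04 days.

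None of this supplies what is missing: an instruction to keep collecting outcomes, and a named analysis set. Data not collected cannot be recovered at analysis.

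**Conclusion.** The point holds in a limited form. As written, section 14.0 removes randomised participants from the study for post-randomisation reasons, and no section continues their outcome collection or says how they enter the efficacy comparison. Bias follows only if removal is related to outcome and differs by arm. Its size cannot be known from the documents: the illustrations give 0 with equal removal, 0.09 day at 20% v 10%, and 0.5 to 0.6 day under strongly unequal removal. All of them rest on an assumed distribution, an assumed 10 per arm and assumed removal rates.

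A reader might take the half-day figure as the expected bias; it is a what-if, not a prediction. Nor does scoring removed participants 0 do comparable harm, since under the same model it moves the difference by only about 0.04 to 0.07 day. The attrition issue is one of reporting, which the planned table of reasons can resolve. The change is worth making before enrolment because it is cheap.

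**What to change.** **Section 14.0.** Define two events: discontinued from stimulation, and withdrawn from the study. For randomised participants, limit study withdrawal to withdrawal of consent (including voluntary withdrawal) or termination of the study. Leave the grounds for stopping stimulation as they are. After stimulation stops, continue the self-reported timeline or diary for the rest of the 7 days and make the one-month phone call. Take CO only if the participant attends. Ineligibility or an unlocatable motor threshold found before randomisation stays a screening exclusion.

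**Section 12.2.** State that abstinence days, cigarettes and craving are analysed for all randomised participants as assigned. Use the planned table of reasons to report participant-initiated and investigator-initiated attrition separately.

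**Cost.** One paragraph in each section and a little more data collection by phone or diary. The calendar in section 10.5 has no visit without stimulation between baseline and the phone call, so participants who stop attending will lack CO confirmation of reported abstinence. That limitation should be stated.

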15.0 Risks to Subjects

Potential Risks. Investigational Device Exemption: Transcranial Magnetic Stimulation is FDA approval device for depression treatment. It is an investigational device for smoking cessation. The IRB at MUSC (in cooperation with the FDA) has determined repetitive TMS to be a non-significant risk intervention.

Potential Risks of TMS:

Potential risk of a seizure:

The most serious side effect associated with rTMS is the accidental induction of a seizure. Although accidental seizures occur at a frequency of <0.1%, there are factors that may increase the risk of rTMS triggering a seizure such as family history of seizures, alcohol use and previous neurological condition. The risk of seizure induction is also related to the intensity, duration, frequency and rest interval of stimulation as well coil type. To date, 2 outpatients have been reported with seizures at

MUSC since 1997. Both patients received therapeutic treatment with Brainsway H coil. To our knowledge, neuronetic stimulator with the parameters and settings we propose to use does NOT cause seizures.

Potential for scalp discomfort and headaches:

Some people report some mild discomfort when the magnetic pulses are applied over the scalp, and a small number of people (~5%) report headache following rTMS. However, the headaches are temporary and manageable with common over-the-counter pain remedies.

Potential hearing loss:

The discharge of the TMS coil generates a high-energy click that may cause damage to the inner ear. Humans exposed to TMS have shown temporary increases in auditory threshold (especially at high frequencies) lasting at least 5 minutes and less than 4 hours. Foam earplugs can protect against these changes and will be worn during TMS sessions.

Potential changes in cognitive function:

There have been no reports of long-term changes (more than a minute) in cognitive function (memory, attention, etc) in TMS studies. Safety studies specifically looking for these changes did not find any effects of TMS with the exception of one open study in which healthy volunteers were exposed to 150 sequences of TMS at different site of stimulation in a procedure that lasted more than 3 hours. There was a significant decrease in scores on a logical memory test. The stimulation parameters exceeded the recommended safety range and there was no control for patient fatigue or other non-specific effects.

Other potential effects of TMS on brain tissue:

TMS is thought to be safe, with no brain damage, despite extensive use in humans and other animals. We have reported a safety study looking at the MRI scans before and after 2 weeks of daily left prefrontal TMS for depression. No structural changes were found in left prefrontal lobe of patients who received active TMS compared to those who received sham TMS. We have also performed an MRI diffusion imaging study before and after TMS/fMRI study and found no harmful effects of TMS on brain tissue at the site of stimulation.

Safety in case of pregnancy:

This protocol will exclude pregnant women. The risks of using TMS with pregnant women are currently unknown. If you are pregnant, or think you might be pregnant at any point during this study, please inform the investigators and the TMS will be discontinued immediately.

Unknown Risks:

TMS is an experimental procedure that has not been approved by the FDA as a treatment for nicotine craving and it may have unknown side effects. The researchers will let you know if they learn anything that might make you change your mind about participating in the study.

Potential Risks of Nicotine Craving Laboratory Procedures:

Risk of emotional distress:

The procedures proposed in these studies are widely used in research and clinical evaluation procedures and have been shown to be safe.

Risks regarding Confidentiality:

Despite efforts to maintain subjects' anonymity and confidentiality, there is always some minimal risk of people other than the study investigators gaining access to your health information. Every effort will

be made to ensure that your health information will be collected and stored in a manner that ensures the highest level of protection of confidentiality.

16.0 Potential Benefits to Subjects or Others

There will be no direct benefit to the subject. However, it is hoped that the information gained from the study will help in smoking cessation in cancer patients. Smokers may be able to stop smoking from this study trial.

17.0 Sharing of Results with Subjects

If we have significant new findings during the course of the study, we will notify the patient.

